# 6.4. Baseline and Other Summaries and Analyses

#### 6.4.1. Baseline Summaries

## 6.4.1.1. Demographic Characteristics

Demographic characteristics, sex, race/racial designation, and ethnicity, will be summarized for the safety population for each vaccine group and overall.

# 6.4.1.2. Medical History

Each reported medical history term will be mapped to a SOC and PT according to MedDRA. The number and percentage of vaccinated participants having at least 1 diagnosis, overall and at each SOC and PT level, will be summarized by vaccine group and overall, for the safety population.

## 6.4.2. Study Conduct and Participant Disposition

## 6.4.2.1. Participant Disposition

The number and percentage of randomized participants will be included in the participant disposition summary. In addition, the numbers and percentages of participants who received vaccinations (Doses 1 and 2), who completed the follow-up visits (1 month after Dose 2), and who withdrew before each follow-up visit along with the reasons for withdrawal will be tabulated by vaccine group (according to randomized group assignment). The reasons for withdrawal will be those as specified in the database.

Participants excluded from each analysis population will also be summarized separately along with the reasons for exclusion, by vaccine group.

Also, for participants who were originally randomized to BNT162b2, or participants who were originally randomized to placebo but declined BNT162b2 after unblinding, the numbers and percentages of participants who completed the follow-up visits (6-month visit and 12-month visit) and who withdrew from the study will be tabulated. For the participants who were originally randomized to placebo but received BNT162b2 after unblinding, the numbers and percentages of participants who received Dose 3 (first dose of BNT162b2) and Dose 4 (second dose of BNT162b2), who completed the telephone contact (1 month after Dose 4 and 6 month after Dose 4), and who withdrew from the study will be tabulated.

# 6.4.2.2. Blood Samples for Assay

The number and percentage of randomized participants providing blood samples within and outside of protocol-specified time frames will be tabulated separately for each time point.

# 6.4.2.3. E-Diaries

The participants who were vaccinated and completed e-diaries after each dose will be summarized according to the vaccine actually received. Besides the analysis described in Section 6.1.1.1 and Section 6.1.1.2, the summary will also include the numbers and percentages of vaccinated participants not transmitting the e-diary, and transmitting the e-diary for any day in the required reporting period, by received vaccine group for each dose.

The safety population will be used.

# 6.4.3. Study Vaccination Exposure

# 6.4.3.1. Vaccination Timing and Administration

For each dose, the number and percentage of participants randomized and receiving each study intervention within the protocol-specified time frame, as well as before and after the specified time frame, will be tabulated for each vaccine group and overall for all randomized participants. The denominator for the percentages is the total number of randomized participants in the given vaccine group or overall.

In addition, the relation of randomized vaccine to actual vaccine received will be presented as a cross tabulation of the actual vaccine received versus the randomized vaccine.

A listing of participants showing the randomized vaccine and the vaccine actually received at each dose will be presented.

For the participants who were originally randomized to placebo but received BNT162b2 after unblinding, the number and percentage of participants receiving Dose 3 (first dose of BNT162b2) and Dose 4 (second dose of BNT162b2) within the protocol-specified time frame, as well as before and after the specified time frame, will be tabulated.

# 6.4.4. Prior/Concomitant Vaccinations

Each prior/concomitant vaccine will be summarized according to the ATC 4th-level classification. All vaccines received within 28 days before Dose 1 will be listed. The number and percentage of participants receiving each concomitant vaccine after Dose 1 will be tabulated by vaccine group. Summarization will be done for the interval between Dose 1 and 1 month after Dose 2. The safety population will be used.

# 6.4.5. Safety Summaries and Analyses

Local reaction, systemic event, AE, and SAE summaries and analyses are described under Primary Endpoint(s) (Section 6.1).

As safety analysis after unblinding for the purpose to be offered the opportunity to receive BNT162b2 for all participants who originally received placebo from protocol amendment 3, counts, percentages, and associated Clopper-Pearson 95% CIs of the participants reporting the following will be displayed:

- AEs and SAEs reported from Dose 1 to before unblinding (safety population).
- AEs reported after unblinding (participants who originally received BNT162b2 and participants who originally received placebo but declined BNT162b2 after unblinding).
- AEs reported after unblinding and the first dose of BNT162b2 (participants who originally received placebo and received BNT162b2 after unblinding).

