#### 8.2.2. Electronic Diary

Participants will be required to complete a reactogenicity e-diary through an application (see Section 8.14) installed on a provisioned device or on the participant's own personal device. All participants will be asked to monitor and record local reactions, systemic events, and antipyretic medication usage for 7 days following administration of the study intervention. All participants who originally received placebo and then received BNT162b2 under protocol amendment 3 and onwards, will not complete a reactogenicity e-diary but will have their local reactions and systemic events collected and reported as AEs in accordance with Section 8.3.2.

The reactogenicity e-diary allows recording of these assessments only within a fixed time window, thus providing the accurate representation of the participant's experience at that time. Data on local reactions and systemic events reported in the reactogenicity e-diary will be transferred electronically to a third-party vendor, where they will be available for review by investigators and the Pfizer clinicians at all times via an internet-based portal.

At intervals agreed to by the vendor and Pfizer, these data will be transferred electronically into Pfizer's database for analysis and reporting. These data do not need to be reported by the investigator in the CRF as AEs.

Investigators (or designee) will be required to review the reactogenicity e-diary data online at frequent intervals as part of the ongoing safety review.

The investigator or designee must obtain stop dates from the participant for any ongoing local reactions, systemic events, or use of antipyretic medication on the last day that the reactogenicity e-diary was completed. The stop dates should be documented in the source documents and the information entered in the CRF.

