# 8.3.1. Time Period and Frequency for Collecting AE and SAE Information

The time period for actively eliciting and collecting AEs ("active collection period") for each participant begins from the time the participant provides informed consent, which is obtained before the participant's participation in the study (ie, before undergoing any study-related procedure and/or receiving study intervention), through and including Visit 7 for the clinical laboratory subset and Visit 5 for the standard participants. In addition, any AEs occurring up to 48 hours after each subsequent blood draw must be recorded on the CRF.

SAEs will be collected from the time the participant provides informed consent to approximately 12 months after Dose 2 of study intervention (Visit 9 for the clinical laboratory subset, Visit 7 for the standard participants).

Confirmed COVID-19 diagnosis (SARS-CoV-2 positive test) will be collected as an AESI from the time the participant provides informed consent until study completion (Visit 9 for the clinical laboratory subset, Visit 7 for standard participants) (see Section 8.3.8).

Additionally, for those participants who originally received placebo but go on to receive BNT162b2 at Vaccinations 3 and 4, AEs will be collected from the time the participant provides informed consent (for receipt of Vaccinations 3 and 4) through and including Visit 103. SAEs and confirmed COVID-19 diagnosis (SARS-CoV-2 positive test) will be collected from the time the participant provides informed consent (for receipt of Vaccinations 3 and 4) to approximately 6 months after Dose 2 of BNT162b2 (Visit 104).

Follow-up by the investigator continues throughout and after the active collection period and until the AE or SAE or its sequelae resolve or stabilize at a level acceptable to the investigator and Pfizer concurs with that assessment.

For participants who are screen failures, the active collection period ends when screen failure status is determined.

If the participant withdraws from the study and also withdraws consent for the collection of future information, the active collection period ends when consent is withdrawn.

If a participant definitively discontinues or temporarily discontinues study intervention because of an AE or SAE, the AE or SAE must be recorded on the CRF and the SAE reported using the Vaccine SAE Reporting Form.

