#### 8.11.1.8. Visit 7 – 1-Month Follow-up Visit (28 to 35 Days After Visit 4)

- Record AEs as described in Section 8.3.
- Record nonstudy vaccinations as described in Section 6.5.
- Confirm details of any of the prohibited medications specified in Section 6.5.1 received by the participant if required for his or her clinical care.
- Discuss contraceptive use as described in Section 10.4.
- Collect a blood sample (approximately 25 mL) for immunogenicity testing.
- Ask the participant to contact the site staff or investigator if a medically attended event (eg, doctor's visit, emergency room visit) or hospitalization occurs.
- Ask the participant to contact the site staff or investigator (this could be via the COVID-19 illness e-diary) immediately if he or she experiences any symptoms as detailed in Section 8.13.
- Schedule an appointment for the participant to return for the next study visit.
- Complete the source documents.
- The investigator or an authorized designee completes the CRFs.

#### 8.11.1.9. Between Visits 7 and 8

All participants will be contacted by the site and unblinded to study intervention allocation to allow placebo recipients the opportunity to receive BNT162b2 as part of the study. If the participant originally received placebo and wants to receive BNT162b2, he or she will follow the procedures in Section 8.16 and the SoA in Section 1.3.3.

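### SAP 6.4.5 plans post-unblinding AE percentages for participants whose general nonserious AE collection has already ended, and a crossover AE percentage under a different AE definition

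*SAP*

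**What the plan says.** SAP 6.4.5 introduces three displays with one statistic: counts, percentages and Clopper-Pearson 95% CIs. The first covers AEs and SAEs from Dose 1 until unblinding in the safety population. The second is "AEs reported after unblinding (participants who originally received BNT162b2 and participants who originally received placebo but declined BNT162b2 after unblinding". The third is "AEs reported after unblinding and the first dose of BNT162b2 (participants who originally received placebo and received BNT162b2 after unblinding". The second and third name only AEs. They give no end date, no restriction by event type and no remark on how the events were collected.

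Protocol 8.3.1 runs active AE collection "through and including Visit 7 for the clinical laboratory subset and Visit 5 for the standard participants", which is the 1-month visit. Three streams continue beyond it:

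- After blood draws, "any AEs occurring up to 48 hours after each subsequent blood draw must be recorded on the CRF".
- For serious events, "SAEs will be collected from the time the participant provides informed consent to approximately 12 months after Dose 2 of study intervention".
- Confirmed COVID-19 is collected as an AESI until study completion.

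Protocol 8.11.1.9 and 8.11.2.6 place unblinding between the 1-month and 6-month visits: "All participants will be contacted by the site and unblinded to study intervention allocation".

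For placebo recipients who cross over, Protocol 8.3.1 collects all AEs from the new consent through Visit 103, and SAEs and confirmed COVID-19 through Visit 104. Protocol 8.2.2 says that they "will not complete a reactogenicity e-diary but will have their local reactions and systemic events collected and reported as AEs". Of the e-diary data in the original phase, the same section says: "These data do not need to be reported by the investigator in the CRF as AEs". Protocol 9.4.2 asks for a separate summary of AEs and SAEs in crossover recipients.

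**The concern.** A percentage of participants with an AE can be read as a rate only if AEs were sought throughout the interval. For original BNT162b2 recipients and placebo decliners, the post-unblinding interval begins after general AE collection has stopped. The denominator is everyone under follow-up, while the numerator can hold nonserious events (other than COVID-19) from only a few days. A low percentage with a narrow exact interval would look like evidence of a quiet safety profile when most of the events it seems to count were not being sought.

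The crossover display departs in the other direction. It counts reactions as AEs, whereas the main AE table for the original two doses rests on a phase in which those reactions went to the e-diary. A reader who puts the two crossover doses beside the two original doses would be comparing percentages built on different definitions. At stake is the readability of the post-unblinding safety section, including the separate crossover summary promised in Protocol 9.4.2.

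**Working it through.** The documents state no figure for this analysis, so there is none to reproduce. The check compares collection windows and then illustrates their effect.

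**1. Original BNT162b2 recipients and decliners.** Inputs: 1-month visit 28 to 35 days after Dose 2, 12-month visit 350 to 378 days after Dose 2 (Protocol 1.3.1 and 1.3.2), and 48 hours after each later draw (8.3.1).

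- From the 1-month to the 12-month visit: 350 − 35 = 315 days to 378 − 28 = 350 days.
- Collection of nonserious AEs other than confirmed COVID-19: 2 draws × 48 hours = 4 days at most.
- Relative to that span: 4/350 = 1.1% to 4/315 = 1.3%. The span after unblinding is somewhat shorter, because unblinding falls at an unstated time after the 1-month visit.

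**2. Crossover recipients.** Inputs: Visit 102 at 19 to 23 days after Visit 101, Visit 103 at 28 to 35 days and Visit 104 at 175 to 189 days after Visit 102 (Protocol 1.3.3).

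- All AEs, Vaccination 3 to Visit 103: 19 + 28 = 47 to 23 + 35 = 58 days, continuous.
- SAEs and confirmed COVID-19, Vaccination 3 to Visit 104: 19 + 175 = 194 to 23 + 189 = 212 days.
- Against the 4 days in step 1: 47/4 = 11.8 to 58/4 = 14.5 times as long, for nonserious AEs other than confirmed COVID-19.

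The original-phase window, Dose 1 to 1 month after Dose 2, has the same nominal length: 19 + 28 = 47 to 23 + 35 = 58 days. Only the AE definition and the way events are elicited differ, which is why the two percentages are easily set side by side.

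**3. Effect of the windows alone.** Suppose every group has the same 30-day risk *r* of a nonserious AE, with a constant hazard and no reactogenicity. The expected share with a recorded event over *d* days of collection is 1 − (1 − *r*)^(*d*/30). The values of *r* are assumptions, since the documents give none.

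| Assumed *r* | *d* = 4 days | *d* = 47 to 58 days |
|---|---|---|
| 5% | 0.7% | 7.7 to 9.4% |
| 10% | 1.4% | 15.2 to 18.4% |
| 20% | 2.9% | 29.5 to 35.0% |
| 30% | 4.6% | 42.8 to 49.8% |

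Identical underlying risk therefore gives displayed percentages about ten times apart, before any vaccine reaction is counted.

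**4. Apparent precision.** If none of the 120 participants planned for BNT162b2 had a recorded event, the Clopper-Pearson upper limit would be 1 − 0.025^(1/120) = 3.0%, so the interval would be 0 to 3.0%. The zero count is hypothetical; SAEs and COVID-19 would add to it. The interval carries sampling error only and takes no account of days without collection.

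**The case against.** The strongest reply is that the SAP compares nothing here. Section 6.4.5 lists separate displays with named populations and plans no difference or p-value, and Protocol 9.4.2 keeps the crossover summary separate. A reader might infer a planned side-by-side safety comparison; the documents do not support that. This part of the reply stands. It does not rescue the second display, which cannot be read as an AE rate even alone.

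Second, collection has not closed altogether. SAEs and confirmed COVID-19 are collected throughout, and COVID-19 illness and convalescent visits record AEs as appropriate (Protocol 8.13.1, 8.13.2). To read the percentage as pure artefact would go too far. The 4-day limit applies only to nonserious AEs other than confirmed COVID-19.

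Third, SAP 3.1.1.4 says that AE reporting follows the specific reporting period and that AEs are summarised by SOC and PT. That supplies an implied end for the crossover display, and PT rows, if used in 6.4.5, would show individual reactions. Any overall AE row would still pool them. For the other set, the general AE reporting period is over before the display begins.

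Fourth, crossover reactions are real vaccine reactions, and the original phase is not wholly free of them: acute reactions within 30 minutes go on the AE CRF (Protocol 8.2), and e-diary events need not be reported as AEs but are not barred. All true; the issue is the change of definition.

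Finally, SAEs to 12 months and an AESI listing are already planned (SAP 6.1.1.4, 6.1.1.3.2), so part of the remedy is relabelling.

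**Conclusion.** The point holds as a defect in a supplementary descriptive display. As written, SAP 6.4.5 gives original BNT162b2 recipients and decliners an AE percentage that is dominated by non-collection: at most about 4 days of nonserious AE recording apart from confirmed COVID-19. It gives crossover recipients a percentage built on about 47 to 58 days of active collection with reactions included. The primary AE and SAE estimands are unaffected.

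The window lengths follow from the visit schedule, with unblinding placed where Protocol 8.11.1.9 and 8.11.2.6 put it. The percentages in the illustration rest on assumed risks and a constant hazard.

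Two further inferences are tempting but unsupported. One is that the crossover percentage must be very high. The documents give no reaction rate, and crossover reactions are elicited under Protocol 8.3.2, which prefers open-ended questioning, without a daily prompted diary. The other is that crossover AEs become comparable with original-phase AEs once solicited-type events are removed. Crossover is unblinded and self-selected, allows eligibility exceptions (8.16.1), and has no 1- or 2-week visits and normally only a telephone contact at 1 month.

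**What to change.** In SAP 6.4.5:

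1. For original BNT162b2 recipients and placebo decliners, replace the post-unblinding AE display with SAEs and AESIs after unblinding, and list the AEs recorded within 48 hours of a blood draw separately.
2. For crossover recipients, use separate displays: AEs from Vaccination 3 through Visit 103, and SAEs and AESIs from Vaccination 3 through Visit 104.
3. Within the crossover AE display, show local and systemic events of the solicited types with onset on Days 1 to 7 after each dose separately from all other AEs.
4. Label each display with its collection window, and state that the sets are not to be compared with each other or directly with the main AE table.

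The change uses data already on the CRF and leaves study conduct and collection as they are. Its cost is a preferred-term and onset-day rule for the solicited-type events and a few re-cut tables.

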# 7. ANALYSES TIMING

# 7.1. Analysis Timing

Statistical analyses will be carried out when the following data are available:

• Primary analysis: complete safety and immunogenicity data through 1 month after Dose 2 from all participants.

An interim summary at different time points may be considered to support internal decisions for additional visits and to support regulatory interactions.

The study's final analysis will be performed when all participants have completed the study and all immunogenicity and safety data are available.

## 7.2. Data Monitoring Committee or Other Independent Oversight Committee

An external DMC will be utilized for this study and will review cumulative unblinded safety data throughout the study in accordance with the charter.

The recommendations made by the DMC to alter the conduct of the study will be forwarded to the appropriate Pfizer personnel for final decision. Pfizer will forward such decisions, which may include summaries of aggregate analyses of safety data, to regulatory authorities, as appropriate.

# 9. APPENDICES

## Appendix 1. List of Abbreviations

Abbreviation	Term
AE	adverse event
ALT	alanine aminotransferase
AESI	adverse event of special interest
AST	aspartate aminotransferase
ATC	Anatomic Therapeutic Chemical
BLQ	below the level of quantitation
BUN	blood urea nitrogen
CI	confidence interval
COVID-19	coronavirus disease 2019
CRF	case report form
DMC	data monitoring committee
e-diary	electronic diary
GM	geometric mean
GMFR	geometric mean fold rise
GMT	geometric mean titer
ICD	informed consent document
IWR	interactive web-based response
LLOQ	lower limit of quantitation
МСН	mean corpuscular hemoglobin
МСНС	mean corpuscular hemoglobin concentration
MCV	mean corpuscular volume
MedDRA	Medical Dictionary for Regulatory Activities
MHLW	Ministry of Health, Labor and Welfare
N	nucleoprotein
N/A	not applicable
N-binding	SARS-CoV-2 nucleoprotein-binding
NAAT	nucleic acid amplification test
non-S	nonspike protein
PRT	protocol
PT	preferred term
RBC	red blood cell
RCDC	reverse cumulative distribution curve
RNA	ribonucleic acid
SAE	serious adverse event
SAP	statistical analysis plan
SARS-CoV-2	severe acute respiratory syndrome coronavirus 2
SoA	schedule of activities
SOC	system organ class

Abbreviation	Term
SOP	standard operating procedure
ULN	upper limit of normal
WBC	white blood cell

# Appendix 1. List of Abbreviations
